a “woman” word [e.g., female] or an “object” word [e.g., tool] appears on the screen vs. pressing “e” whenever a “woman” word or a “human” word [e.g., person] appears). Making a response is easier (and thus faster) when closely related constructs share the same response key. Therefore, quicker response times when woman and object (vs. human) words are paired represents more implicit objectification. We expect intoxication to cause faster reaction times when women and object words are paired and slower reaction times for pairings of women and human words.

The Other-Objectification Questionnaire (modified from Grabe, Rutledge, Cook, Andersen, & Arndt, 2005; Curran, 2005), which assesses the frequency (6=very frequently, 1=never) with which the male participant objectified the female confederate (e.g., I focused more on her body than our conversation). Scores are averaged with higher scores representing more objectification of women. We expect intoxication to cause more weight to be placed on women’s objectifying compared to human attributes in men’s evaluations.

Sexual aggression. To assess sexual aggression, participants will complete the Laboratory Analogue of Sexual Aggression (Parrott et al., 2012) based on Hall, Hirschman, and Olivier (1994). Following the ostensible interaction in which the participant learns that the female participant dislikes media with sexual content, men then select one clip—containing either a man and a woman having sexual intercourse or a similar clip without sexual content—for the woman to watch based on still shots and synopses. Choosing the sexual (vs. non-sexual) clip represents sexual aggression. Although perpetrators may justify their choices (e.g., reasoning that the woman may not like sexual content in general, but that she would like this sexual content in particular), such responses fall under the CDC definition of sexual violence (i.e., subjecting a woman to an unwanted sexual experience). Validity of the paradigm is supported by expected positive associations between selection of the sex video and self-reported history of sexual aggression perpetration, adversarial heterosexual beliefs, hostility toward women, and hostile sexism (Parrott et al., 2012). We expect intoxication to cause more sexual aggression.

Study 2: Self-Objectification and Alcohol-Involved Sexual Victimization (Aim 2)

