sexual victimization history (women), as well as, sex-related alcohol expectancies and rape myth acceptance to emerge as significant moderators of the relation between objectification and assault. Specifically, we expect sexual objectification to predict sexual aggression perpetration in men and self-objectification to predict victimization risk in women, but these effects should be particularly pronounced for people with a history of sexual assault (perpetration in men, victimization in women), as well as for people who endorse more rape myths and those who hold higher sex-alcohol expectancies. All continuous variables (i.e., all variables except the dichotomous measure of aggression in Study 1) will be grand mean centered prior to creating the interaction terms to improve interpretability as recommended by Cohen, Cohen, West, and Aiken (2003). The process will then be repeated for the measures of objectification and the moderator variables. Given the correlations between the moderator variables, the two-way interactions will be examined individually first. All significant interactions will be added to the model simultaneously to examine whether moderation remains. Type I error inflation across models will be controlled for using the Scheffe correction and no effects that explain less than 1% of the total variance will be considered important, regardless of statistical significance.

Missing data. Because the proposed studies are lab experiments, large amounts of missing data are unexpected. Data missing due to equipment malfunctions are missing completely at random (MCAR) and data missing due to nonresponses from participants will be considered missing at random (MAR). The methods for dealing with MCAR and MAR data are full information maximum likelihood (FIML) and multiple imputation (Enders, 2010). By default, Mplus uses FIML, so FIML will be used here for all analyses. Also, bias analyses will be conducted to examine demographics of people who participated in our study compared to people who were recruited for the study, but did not meet the inclusion criteria or who did not agree to participate in our study.

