Statistical power. A single mediator model with standardized coefficients of $a=b=.26$ (approximately halfway between a small and medium effect as defined by Cohen, 1988) and $ab=.0676$ requires 148 participants to have statistical power of .80 for the bias-corrected bootstrap test (Fritz & MacKinnon, 2007). The mediation models for Aims 1 and 2 have two mediators entered serially (i.e., attentional impairment and objectification), however, with multiple measures of objectification. When X is dichotomous and two mediators are entered serially, 150 participants provide approximately .82 power to find a standardized mediated effect between .05 and .10 using the bias-corrected bootstrap test (Taylor, MacKinnon, & Tein, 2008) – a standardized mediated effect made up of three medium effects ($a=b_1=b_2=.39$) is equal to .06. Using multiple objectification measures slightly decreases individual effects due to partialling, but this will not affect the power calculations because they are based on partial effects. Research has found that alcohol predicts 10% of the objectification variance, and alcohol and objectification together predict 22% of the sexual assault variance ([name], et al., 2014; see also Haikalis et al., 2015). These are medium and large effects, so sample sizes of 150 (Study 1) and 210 (Study 2) will provide adequate power to test Aims 1 and 2. The power analyses for Aim 3 are different because they involve moderation effects in the context of mediation, which Hayes (2013) terms a conditional process model. An issue with detecting moderator effects is the small amount of variance explained by an interaction relative to a main effect (McClelland & Judd, 1993). No work on power for conditional process models has been conducted, but using G*Power (Faul, Erdfelder, Lang, & Buchner, 2007) to conduct a sensitivity analysis found that a sample size of 150 (Study 1) would provide .80 power to detect a moderation effect of $f^2 = .053$ (slightly larger than a small effect of $f^2 = .02$, Cohen, 1988) when the moderation term, a main effect term (for the 2 alcohol intoxication conditions), and two additional predictors are included in the model. A second sensitivity analysis found that a sample size of 210 (Study 2) would provide .80 power to detect a moderation effect of $f^2 = .044$ when the moderation term being tested, two main effects terms (one for the 2 objectification conditions and one for the 2 alcohol conditions), two interaction terms (between the intoxication

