
and objectification factors), and two additional predictors are included in the model. This is equivalent to testing moderation of the relation between objectification and aggression/victimization risk in the mediation models, so sample sizes of 150 (Study 1) and 210 (Study 2) will allow adequate power to test Aim 3 (Figure 3).

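### Study 1's .80 power to detect moderation of the objectification-to-aggression path comes from a continuous-outcome F test, but aggression is a single yes/no choice

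*SAP*

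**What the plan says.** The Statistical power section of the SAP treats Aim 3 separately from Aims 1 and 2. It first concedes: "No work on power for conditional process models has been conducted". It then turns to a G*Power sensitivity analysis and reports that "a sample size of 150 (Study 1) would provide .80 power to detect a moderation effect of" f² = .053. The model contains the moderation term, a term for alcohol condition and two further predictors. The section closes by carrying the result over to the planned analysis: "This is equivalent to testing moderation of the relation between objectification and aggression/victimization risk in the mediation models". From this it concludes that 150 men give adequate power for Aim 3.

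The SAP's Aim 3 moderation text expects perpetration history, sex-related alcohol expectancies and rape myth acceptance "to emerge as significant moderators of the relation between objectification and assault". The same text sets the Study 1 outcome apart when it describes the continuous measures as "all variables except the dichotomous measure of aggression in Study 1". The protocol (Study 1, Sexual aggression) defines that outcome: "Choosing the sexual (vs. non-sexual) clip represents sexual aggression".

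**The concern.** Cohen's f² with a count of predictors belongs to multiple regression with a continuous outcome. A yes/no outcome carries less information per participant, and how much less depends on how often the event occurs. The SAP names no link function for aggression, no expected clip-choice rate, no odds ratio and no conversion of f² to a binary outcome. The claimed equivalence therefore has nothing behind it on this path.

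Three of the four Study 1 moderators act on the path that ends in the clip choice. Only chronic objectification of women is placed elsewhere, on the path from impaired attention to objectification. The f² = .053 calculation is the only quantitative support for Study 1's Aim 3 adequacy statement. If the figure does not transfer, a null moderation result on this path cannot be read against a known detectable effect.

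**Working it through.** **Step 1: reproduce the SAP's figure.** Inputs from the Statistical power section: N = 150, f² = .053, one tested term among four predictors. Alpha is not stated there; .05 is assumed.

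- Noncentrality: λ = f² × N = .053 × 150 = 7.95.
- Degrees of freedom: 1 and 150 − 4 − 1 = 145.
- Power = P(noncentral F(1, 145; 7.95) > 5% critical value) = **.7998**.
- Solving for power .80 gives f² = .0530.

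The variants do not match: a one-sided test gives f² = .0416 and two numerator degrees of freedom give .0656. The number of covariates hardly matters (.0530 to .0531 for 1 to 10 predictors). The SAP does not name the test family, but this match identifies it as the linear F test.

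**Step 2: apply the same f² to a yes/no outcome.** The documents give no inputs for this, so the following are assumptions:

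- 75 men per arm, with alcohol coded ±1.
- Objectification O and moderator W independent and standard normal.
- Latent tendency Y* = b_A·A + b_O·O + b_W·W + b_I·(O×W) + N(0,1). The sexual clip is chosen when Y* exceeds a cut set to give the clip-choice rate (10–50%).
- One-degree-of-freedom likelihood-ratio test of O×W in a logistic model, alpha .05.

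Two readings of f² = .053 are possible:

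- **Latent scale:** b_I² = .053.
- **Observed scale:** b_I is chosen so that O×W has a partial f² of .053 in a linear regression of the 0/1 choice. This implies a larger latent effect. With no main effects, latent f² runs from about .096 at 50% choice to .159 at 10%, that is .096/.053 = 1.8 to .159/.053 = 3.0 times as large.

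Main effects are set in three ways: none; 22% of latent variance split equally between alcohol and objectification (b_A² + b_O² = .22/.78 = .282, so .141 each), borrowing the SAP's 22% figure; or a coefficient of .3 each for alcohol, objectification and moderator.

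| Scale of f² = .053 | Main effects | Clip-choice rate | Power |
|---|---|---|---|
| Latent | none, or 22% split | 10–50% | about .28–.58 |
| Observed 0/1 | none, or 22% split (moderator none) | 20–50% | about .77–.85 |
| Observed 0/1 | .3 each, moderator included | 30 / 20 / 10% | about .73 / .61 / .40 |

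**Step 3: checks.** With the outcome left continuous and no main effects, this kind of simulation gives about .76–.78, so most of the drop on the latent scale comes from the yes/no outcome. Holding the product term's variance fixed in each sample moves cells by a few hundredths; the top of the latent range becomes about .62. These are results for the listed assumptions, not bounds.

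**The case against.** The strongest reply is that f² here means variance explained in the choice as observed. The SAP speaks that way elsewhere: "alcohol and objectification together predict 22% of the sexual assault variance", and "no effects that explain less than 1% of the total variance will be considered important". On that reading the stated .80 roughly survives at 20–50% clip choice in the cases without a moderator main effect, while the low figures need a latent scale that neither document mentions. This stands in part, and it is why no shortfall can be asserted.

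It does not rescue the figure, because the reassurance depends on the moderator having no effect of its own. The protocol's validity evidence for the clip task reports a positive association between choosing the sex video and self-reported perpetration history, which is one of the three moderators concerned. With a modest moderator main effect, observed-scale power falls below .80 at 30% choice and lower, although it stays above .80 at 50%.

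A second reply is that the equivalence sentence follows a list of model terms and may mean only that the predictors match. It also comes after the admission that no power work exists for such models. Both points soften the criticism. But the admission does not mention the type of outcome, and the sentence still ends in a claim of adequate power for Study 1.

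**Conclusion.** The equivalence claim is wrong as written for the Study 1 objectification-to-aggression path. The .80 is a correct continuous-outcome figure applied to a yes/no outcome. This is an unsupported power assumption, not an arithmetic error. Under the assumptions listed, power for the same nominal f² ranges from about .28 to about .85, depending on scale, clip-choice rate and main effects that the SAP leaves unspecified.

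A reader might infer that Study 1 is underpowered for Aim 3. The documents do not support that: they fix neither the scale of f² nor the clip-choice rate, and on the observed scale several plausible settings give about .80. A reader might equally infer that .80 holds whenever 20–50% choose the sexual clip. That is too general, since it fails at 20% and 30% once the moderator has a main effect of the size illustrated.

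The point covers this one path. It does not reach the 148-participant benchmark, the H1c mediation power, moderation of the attention-to-objectification path, or the Study 2 figure, none of which is challenged or confirmed here.

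**What to change.** For the Study 1 objectification-to-aggression moderation only, replace the linear F-test figure with a binary-outcome calculation by simulation. It should use:

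- the logit or probit model that will be fitted;
- an effect given either as f² on a stated scale or as an odds ratio;
- a range of clip-choice rates;
- main effects that include the moderator's own;
- a stated alpha.

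Then restate the power, or the minimum detectable effect, for 150 men. In the closing sentence of the Statistical power section, limit the equivalence and adequate-power wording for Study 1 aggression to what that result supports.

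The cost is one simulation and a few sentences in the SAP, with no extra participants. The downside is that the stated figure for this path may become less favourable.
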